Peripheral artery disease	NPR	ICD10: I739	Co-variate Included in CHA2DS2VASc score
Ischemic heart disease	NPR	ICD10: I20-I25	Co-variate
Myocardial infarction	NPR	ICD10: I21-I22	Co-variate
Angina pectoris	NPR	ICD10: I20	Co-variate
Chronic obstructive pulmonary disease	NorPD	Reimbursement codes: J44 (ICD10) or R95 (ICPC) in ATC group R03	Co-variate
Cancer	NPR	ICD10 codes: C00 to C97	Co-variate Included in Charlson Co-morbidity score
Leukemia	NPR	ICD10 codes: C90-C96	Co-variate Included in Charlson Co-morbidity score
Lymphoma	NPR	ICD10 codes: C80 to C88	Co-variate Included in Charlson Co-morbidity score
AIDS	NPR	ICD10 codes B20 to B24	Co-variate

Variable	data source	Definition	Relevance
			Included in Charlson Co-morbidity score
Thrombocytopenia	NPR	ICD10 codes: D692, D693, D694, D695, D696, D698, D699	Co-variate
Anemia	NPR	ICD10 codes: D65-D67, D680, D681, D682, D683, D684, D685, D686, D688, D689, D50-D53, D55-D59, D60-D64	Co-variate
Hypo/hyperthyroidism	NPR	ICD10 code: E03 / E05	Co-variate
Systemic connective tissue disease	NPR	ICD10 codes: M30 to M36	Co-variate Included in Charlson Co-morbidity score
Peptic ulcer and bleeding	NPR	ICD10 codes: Ulcer K25 to K29. Gastrointestinal bleeding K920/K921/K922	Co-variate Included in Charlson Co-morbidity score
Chronic liver disease and impairment	NPR	ICD10 codes: K70-K77	Co-variate Included in mHASBLED score
Renal impairment	NPR	ICD10 codes: D63.8, E10.2, E11.2, E13.2, I12.0, I13.1, I13.2, N02.x, N03.x, N04.x, N05.x, N07.x, N08.x, N11.x, N14.x, N18.x, N19, Q61.x	Co-variate Used in stratified analyses
Surgery performed in the study period	NPR	All NCSP codes including codes for active surgery	Co-variate. Adjust or exclude for in bleeding outcomes
Imidazol and triazol derivates	NorPD	ATC codes J02AB and J02AC	Co-variate. Interaction

Variable	data source	Definition	Relevance
Low-dose aspirin	NorPD	ATC code: B01A C06	Co-variate Included in mHASBLED score
Immunosuppressive treatments	NorPD	ATC code: L04A	Co-variate
Anti-platelet treatment (non aspirin)	NorPD	ATC code: B01A	Co-variate Included in mHASBLED score
Non-steroidal anti-inflammatory drugs (NSAID)	NorPD	ATC code: M01A	Co-variate. Included in mHASBLED score
Acid secretory drugs	NorPD	ATC code: A02B	Co-variate
Heparin	NorPD	ATC code: B01AB	Co-variate
Anti-arrytmic drugs class iii	NorPD	ATC code C01BD	Co-variate. Interaction
Rifampicin	NorPD	ATC code J04AB	Co-variate. Interaction
Anti-hypertensives	NorPD	ATC code: C02	Co-variate

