CHA ₂ DS ₂ VASc	NPR and NorPD	
 - Chronic Heart Failure by NorPD reimbursement codes for heart failure: I50 (ICD10) or K77 (ICPC). 1 point - Hypertension defined by dispensation of at least one anti-hypertensive drug last year prior to index date (see definition above). 1 point - Diabetes defined by dispensation of at least one anti-diabetes drug last year prior to index date (see definition above). 1 point - Age \geq75 years (2 points) or age 64-74 years (1 point) - Previous stroke, TIA or thromboembolism by ICD10 codes (see definition above). 2 points - Peripheral artery disease (ICD10; I739). 1 point - Gender (male=1 point, female=0 point) 
Total score 0 to 9
	Stroke risk score used as co-variate and effect modifier
Charlson co-morbidity index	NPR and NorPD	
 - Age: \leq41 years (0 point), 41-50 years (1 point), 51-60 years (2 points), 61-70 (3 points), \geq71 years (4 points) - Myocardial infarction. 1 point - Congestive Heart Failure. 1 point - Peripheral Vascular Disease. 1 point - TIA or stroke. 1 points - Dementia. 1 point 	Co-morbidity risk score and co-variate

Variable	data source	Definition	Relevance
		
 - COPD. 1 point - Connective Tissue Disease. 1 point - Peptic ulcer and bleeding 1 point - Diabetes. 1 point - Moderate to severe Chronic Kidney Disease (combined CKD and ESRD). 2 points - Leukemia. 2 points - Lymphoma. 2 points - Solid tumour. 2 points - Liver disease. 3 points - Solid tumour with metastasis. 6 points - AIDS. 6 points Total score from 0 to 37	

Table 5: Additional clinical characteristics to be retrieved for the EMR cohort (cohort 2)

Variable	Data source	Operation definition	Relevance
Height	EMR	Height in centimeters from time point closest to the index date	Co-variate
Weight	EMR	Weight in kilogram from time point closest to the index date	Co-variate
Smoking habits	EMR	Smoking habits retrieved as free text search. Converted to pack-years	Co-variate
Alcohol abuse	EMR	Alcohol abuse search as free text	Co-variate
International normalised ratio	EMR	Retrieve all INR measurements from index to the end of study. Calculated INR mean during the study period	Co-variate. Imputation
Blood haemoglobin	EMR	Retrieve all Hb measurements from index to the end of study. Calculated Hb mean during the study period. Identify episodes of more than 20 g/L fall in hemoglobin	Co-variate. Bleeding endpoint

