S-Creatinine	EMR	Retrieve all s-creatinine measurement from index to the end of study. Calculate eGFR (ml/min) and categorise in CKD stages (1-5)	Co-variate
OAC dosing	EMR	Number of tablets used per days retrieved from dosing instructions. Especially important for warfarin dosing	Co-variate. Imputation and modelling of warfarin exposure in the registry cohort
Blood transfusions	EMR	Number of blood transfusion. More or equal to two transfusion units will be used in the ISTH bleeding definition	For ISTH bleeding outcome

Variable	Data source	Operation definition	Relevance
Fatal bleeding	EMR	Patients that die from bleeding while at hospital	For ISTH bleeding outcome

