2. Symptomatic bleeding in a critical area or organ, such as intracranial, intraspinal, intraocular, retroperitoneal, intraarticular or pericardial, or intramuscular with compartment syndrome (from ICD10 codes in NPR), and/or
3. Bleeding causing a fall in hemoglobin level of 20 g/ L (1.24 mmol/L) or more, or leading to transfusion of two or more units of whole blood or red cells (from EMR data).

Organ system divided analyses (intracranial hemorrhage, gastrointestinal bleeding etc.) will be analyzed separately.

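### Section 9.3.1 makes surgery at any time in the study period a covariate or exclusion for bleeding outcomes, so an operation for a bleed can remove or condition on the outcome

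*Protocol*

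**What the plan says.** Section 9.3.1 of the protocol is headed as baseline characteristics. Table 4, which applies to cohorts 1 and 2, has a row "Surgery performed in the study period", defined as "All NCSP codes including codes for active surgery". Its relevance entry makes it a covariate and adds "Adjust or exclude for in bleeding outcomes".

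Table 5, for the EMR cohort (cohort 2) only, has three laboratory rows with a follow-up window, each labelled as a covariate:

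- **INR:** "Retrieve all INR measurements from index to the end of study. Calculated INR mean during the study period". Also marked for imputation.
- **Haemoglobin:** "Retrieve all Hb measurements from index to the end of study. Calculated Hb mean during the study period". Also marked as a bleeding endpoint.
- **Creatinine:** "Retrieve all s-creatinine measurement from index to the end of study". Converted to eGFR and CKD stage.

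Section 9.3.4.2 uses haemoglobin again in the ISTH outcome: "Bleeding causing a fall in hemoglobin level of 20 g/ L (1.24 mmol/L) or more".

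Section 9.7 bases the propensity scores on demographics, medical history and baseline co-medication, and section 9.7.2 adjusts the Cox models for baseline covariates. Neither section drops or re-dates the four variables above.

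**The concern.** A covariate or exclusion measured after treatment starts can be a consequence of the treatment, of the outcome, or of both. Surgery is the clearest case. An operation to evacuate an ICH, or to stop another bleed, carries a surgical code dated in the study period. Under the Table 4 rule that code can take the patient out of the bleeding analysis, or enter the model as a predictor of the event that caused it.

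Because Table 4 covers cohort 1, the rule can reach the nationwide ICH comparison. At stake are the absolute ICH rates, which are themselves part of the primary objective, and possibly the rate ratio. The wording also leaves open whether to adjust or to exclude, and the two can give different answers.

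The laboratory rows raise the same question for cohort 2. Follow-up haemoglobin is both a covariate and part of the outcome. INR and creatinine measured on treatment are not baseline values.

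**Working it through.** **1. Timing, row by row**

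| Variable | Cohorts | Window in 9.3.1 | Stated use |
|---|---|---|---|
| Surgery | 1 and 2 | Calendar study period, so before and after index | Covariate; adjust or exclude in bleeding outcomes |
| INR | 2 | Index to end of study, mean | Covariate; imputation |
| Haemoglobin | 2 | Index to end of study, mean | Covariate; bleeding endpoint |
| Creatinine, CKD stage | 2 | Index to end of study | Covariate |
| Height, weight | 2 | Value nearest index | Covariate |

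Other items in the same tables are tied to index (height and weight; several HAS-BLED components use the year before index). The follow-up windows are therefore a choice made row by row. Hip or knee replacement shortly before index is already a separate exclusion in section 9.2.2.

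**2. The plan's own figure, for scale**

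Table 10, dabigatran against warfarin, N = 6,930 per group, ICH risk 1.23%, relative risk 1.00:

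- Expected events per group = 0.0123 × 6,930 = 85.24.
- SE(log RR) = √[2 × (1/85.24 − 1/6,930)] = 0.152.
- Interval = exp(±1.96 × 0.152) = (0.74, 1.35), as printed.

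**3. Excluding operated patients**

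Let p be the true ICH risk, s1 the probability of surgery in patients with ICH, and s0 that in patients without. The risk among those kept is

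p(1 − s1) / [p(1 − s1) + (1 − p)(1 − s0)].

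The warfarin risk p = 1.23% is from section 9.5. All surgery probabilities are assumptions, because the protocol gives none. With s0 = 20% in both groups and s1 = 50% on warfarin:

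0.0123 × 0.5 / (0.0123 × 0.5 + 0.9877 × 0.8) = 0.00615 / 0.79631 = 0.77%.

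| s1 warfarin / NOAC (s0 = 20% in both) | Warfarin risk kept | True RR 1.00 becomes | True RR 0.60 becomes |
|---|---|---|---|
| 20% / 20% | 1.23% | 1.00 | 0.60 |
| 50% / 50% | 0.77% | 1.00 | 0.60 |
| 50% / 40% | 0.77% | 1.20 | 0.72 |
| 40% / 50% | 0.93% | 0.84 | 0.50 |
| 50% / 30% | 0.77% | 1.40 | 0.84 |
| 30% / 50% | 1.08% | 0.72 | 0.43 |

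Surgery in non-bleeders matters too. With s1 = 50% in both groups but s0 = 25% on warfarin and 20% on NOAC, a true RR of 1.00 becomes 0.772/0.823 = 0.94.

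**4. Adjusting for surgery instead**

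The same expected counts, stratified by surgery and pooled by Mantel–Haenszel, with a true RR of 1.00:

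- s1 50% / 40%, s0 20% in both: stratum ratios are 1.20 (not operated) and 0.80 (operated); pooled 1.00.
- s1 50% in both, s0 25% / 20%: stratum ratios are 0.94 and 1.24; pooled 1.08.

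So adjustment can be harmless where exclusion is not, and the reverse can also happen.

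**5. Follow-up mean haemoglobin**

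This was simulated with 400,000 patients, an assumed 5% bleed risk and a true RR of 0.60. The sample estimate adjusted for baseline haemoglobin was 0.587. Replacing baseline by follow-up mean haemoglobin gave 0.588 to 0.602 when a bleed lowers the mean by 2.5 to 12.5 g/L. Adding the follow-up mean to baseline haemoglobin gave 0.592 to 0.764. With a true RR of 1.00 nothing moved materially.

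**The case against.** Several points limit the reach of the concern.

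- **Sections 9.7 and 9.7.2 speak of baseline covariates**, and section 9.7.1 mentions no surgery rule for ICH. This stands as evidence of intent, but it leaves a contradiction with Table 4 rather than resolving it.
- **The surgery rule may be meant for peri-operative bleeds**, since the cited ISTH definition is for non-surgical patients. That is plausible for a cohort 2 secondary outcome. It does not explain a rule for both cohorts, on any surgical code, with no time order. ICH is defined by diagnosis codes alone.
- **Equal surgery shares leave the ratio nearly unbiased**, and operated non-bleeders leave the denominator as well. Both are correct and are built into the calculation above: if bleeders and non-bleeders are operated on equally often, nothing changes.
- **Table 5 concerns only cohort 2**, a pilot that depends on access to records and is analysed separately. This stands. Post-index INR for warfarin dose modelling and post-index haemoglobin for the endpoint are also proper uses.

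A reader might infer more than the text supports:

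- **That follow-up INR enters the propensity score and separates the arms.** Section 9.7 does not name INR, and a covariate label in a retrieval table does not make it a score term.
- **That the renal subgroup is defined by follow-up creatinine.** The row marked for stratified analyses is a diagnosis-code variable in Table 4. Creatinine is marked only as a covariate.
- **That no pre-index laboratory value will exist.** Section 9.4 starts the EMR extraction in 2009 and lists laboratory values without a window. Only Table 5 restricts them to index onward.

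**Conclusion.** The point holds in two parts of unequal strength.

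The firm part is the surgery row. As written it permits person-level exclusion or adjustment on operations that follow index and may follow the bleed, in both cohorts, and it conflicts with the baseline covariates of section 9.7. Under exclusion, absolute ICH rates are too low if bleeders are operated on more often than non-bleeders. The ratio can move either way: over the assumed range with equal surgery in non-bleeders, a true 1.00 becomes anything from 0.72 to 1.40. It is nearly unbiased if surgery is equally likely in both groups, among bleeders and among non-bleeders. These figures illustrate the mechanism and are not estimates, because the protocol gives no surgery rates.

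The secondary part is conditional and confined to cohort 2. If INR, haemoglobin or creatinine from Table 5 is used for adjustment, matching or subgrouping, it is a post-treatment variable. For mean haemoglobin used alone, the simulated effect on the treatment ratio is negligible.

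The precision tables in section 9.5 are unaffected.

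**What to change.** Align section 9.3.1 with section 9.7 before the data are extracted:

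1. Limit the surgery covariate to operations before index.
2. In the main bleeding analyses, do not adjust for post-index surgery or exclude persons because of it.
3. Address peri-procedural bleeding in a sensitivity analysis that censors at, or classifies by, surgery dated before the bleed. Do not rely on an elective flag, because the NPR variables listed in section 9.4 include none.
4. In Table 5, use the last haemoglobin and creatinine on or before index as covariates.
5. Keep post-index haemoglobin for the ISTH endpoint only, and INR for warfarin exposure modelling and description only.

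The cost is a change to the covariate tables and to the laboratory window. No new data source is needed, since the EMR extraction already reaches back to 2009. The drawback is that some cohort 2 patients will have no pre-index laboratory value and will fall under the missing-data rules of section 9.7.3.

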8.2 Secondary objectives

- To assess the incidence rates of:

- overall stroke (ischemic, hemorrhagic, other unspecified) and systemic embolism outcomes;
- myocardial infarction;
- all-cause mortality;
- major bleeding as defined by ISTH and the Cunningham algorithm (in a sub-set of patients; cohort 2)

in OAC naïve NVAF patients who are dispensed individual NOACs for the first time and compare with the corresponding rates in OAC naïve users of warfarin in the overall and in a propensity score matched population.

- To describe and compare demographic and clinical characteristics (age, gender, CHA₂DS₂-VASc and HAS-BLED score, bleeding history, concomitant medications and co-morbidities) as well as drug utilization patterns of NVAF patients who initiated an OAC (NOACs and warfarin) in the study period.

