9.3 Variables

9.3.1 Baseline characteristics

Table 4: Demography and clinical characteristics extracted for cohort 1 and 2

Variable	data source	Definition	Relevance
Age	FRG	Age in year	Co-variate and included in risk scores
Gender	FRG	Male or female	Co-variate and included in risk scores
Origin	FRG	Place of birth categorized as Norway, the Nordic countries, other Europe, rest of the world	Co-variate
Immigration date	FRG	Date of immigration out of Norway	Censoring
Emigration date	FRG	Date of emigration out of Norway	
Date of death	FRG	Date of death	Censoring and outcome variable
Alcoholism	NPR	ICD10 codes: E244, G312, G621, G721, I426, K860, O354, Z714, Z721, E52, K70, T51	Co-variate
Chronic kidney disease (CKD)	NPR	ICD10 code: N18 as an option 1 to define CKD Expanded list of codes to define CKD will be considered as an option 2, This list is being used for another ongoing study and is based on the approaches by Fleet et al (8)., Nielsen et al (9). and Weir et al (10). that in addition to identifying patients from the option 1 will allow an inclusion of patients with cystic kidney disease, unspecified kidney failure, chronic or unspecified nephritic syndrome, nephrotic syndrome, recurrent and	Co-variate

Variable	data source	Definition	Relevance
		persistent hematuria, nephropathy (diabetic, hypertensive, hereditary), chronic tubulo-interstitial nephritis, diabetes mellitus with kidney complications as having renal dysfunction (see Annex 3). The option 2 will be further clarified.	
End stage renal disease	NPR	ICD10 code: N185 or procedure codes KAGD40 (hemodialysis chronic) or KAS (renal transplant)	Co-variate Hemodialysis included in mHASBLED score
Congestive heart failure	NorPD	NorPD reimbursement codes for heart failure: I50 (ICD10) or K77 (ICPC) in ATC code group C	Co-variate. Included in CHA2DS2VASc score
Dementia	NPR	ICD10 codes F00-F04, G30	Co-variate
Diabetes	NorPD	ATC code A10A or A10B	Co-variate
Ischemic stroke	NPR	ICD10 codes: I63	Co-variate
Hemorrhagic stroke	NPR	ICD10: I60-62	Co-variate Included in mHAS-BLED score
TIA	NPR	ICD10 code: G45	Co-variate Included in CHA2DS2VASc score
Stroke&tia	NPR	ICD10: I60-I64	Co-variate Included in CHA2DS2VASc score
Thromboembolism	NPR	ICD10: I74	Co-variate

Variable	data source	Definition	Relevance
			Included in CHA2DS2VASc score
Hypertension	NorPD	Reimbursement codes in NorPD in ATC code group C: E10-E13, E15 (ICD10) or K86, K87 (ICPC)	Co-variate Included in mHASBLED and CHA2DS2VASc risk score

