Diuretics	NorPD	ATC code: C03	Co-variate
Beta-blockers	NorPD	ATC-code: C07	Co-variate
Calcium antagonists	NorPD	ATC-code: C08	Co-variate
Renin-angiotensin system drugs	NorPD	ATC-code: C09	Co-variate

Variable	data source	Definition	Relevance
Lipid-modifying drugs	NorPD	ATC-code: C10	Co-variate
Reduced or standard dose NOAC at index	NorPC	Indicator variable whether on reduced (15 mg riva, 2,5 mg api, 110 mg dabi) or standard (20 mg riva, 5 mg api, 150mg dabi) at index dispensation	Co-variate
Prior OAC use	NorPD	Previous OAC use. OAC availability (time of exhaustion of last dispensation) in 365 days prior to index dispensation. From the time of exhaustion of last dispensation and initiation of OAC in study period (> 12 months pre-index)	Co-variate
Previous bleeding hospitalization	NPR	ICD codes listed in section 9.3.4.2	Co-variate Included in mHASBLED
Modified HAS-BLED score	NPR and NorPD	
 - Hypertension defined by dispensation of at least one anti-hypertensive drug (see definition for hypertension above) last year prior to index date. 1 point - Renal impairment as defined by either hemodialysis (procedure code KAGD40) or kidney transplantation (procedure code KAS) or CKD stage 3 and 4 (ICD10 code N183, N184, N185). Expanded list of codes to define CKD will be considered as an option 2, 1 point - Liver impairment (ICD10 K70-K77). 1 point - Stroke during the last year prior to index visit (see definition). 1 point - Prior major bleeding (critical organ) last year before index date (see definition in 9.3.4.2) 1 point 	Bleeding risk score used as co-variate and effect modifier

Variable	data source	Definition	Relevance
		
 - Age \geq 65 years. 1 point - Therapy with either Nonsteroidal Anti-inflammatory Drugs (NSAID M01A) or anti-platelets (B01AC) in the previous year before index date. 1 point - Alcoholism (as defined by ICD10 codes above). 1 point 
Total HAS-BLED score from 0 to 8
	

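### Table 4 miscodes three baseline variables: the CHA2DS2-VASc sex point, the ICD-10 codes for hypertension, and the ATC code for non-aspirin antiplatelets

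*Protocol*

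**What the plan says.** All the entries are in Protocol section 9.3.1, Table 4.

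- **CHA2DS2-VASc.** The sex item is "Gender (male=1 point, female=0 point". The one-point age band is given as "or age 64-74 years (1 point". The row closes with "Total score 0 to 9", and its stated role is "Stroke risk score used as co-variate and effect modifier".
- **Hypertension.** The definition is "Reimbursement codes in NorPD in ATC code group C: E10-E13, E15 (ICD10) or K86, K87 (ICPC". The hypertension items of CHA2DS2-VASc and modified HAS-BLED both refer back to it.
- **Antiplatelets.** The row "Anti-platelet treatment (non aspirin" carries ATC code B01A. The modified HAS-BLED item in the same table is written as "anti-platelets (B01AC) in the previous year before index date".

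Section 8.2 makes the scores a reported result under a secondary objective: "To describe and compare demographic and clinical characteristics (age, gender, CHA₂DS₂-VASc and HAS-BLED score, bleeding history, concomitant medications and co-morbidities". Section 9.6 directs that comorbidity scores be calculated, and co-medications selected by ATC code, from section 9.3.1. Section 9.7 bases the propensity scores on demographics, cardiovascular risk factors, comorbidities and baseline co-medication.

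**The concern.** The protocol does not leave these codes for later. It states them, and section 9.6 sends the programmer to them. Followed as written, they give a stroke risk score with its sex item reversed, a hypertension flag that looks partly for diabetes, and an antiplatelet flag that covers most of the antithrombotic drugs in the study.

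Three uses are exposed: the description and comparison of risk scores (section 8.2), the use of both scores as effect modifiers (Table 4), and the hypertension and antiplatelet covariates offered to the propensity models (section 9.7).

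**Working it through.** **1. Sex item.** The maximum points in the CHA2DS2-VASc row are heart failure 1, hypertension 1, diabetes 1, age 2, stroke/TIA/thromboembolism 2, peripheral artery disease 1 and sex 1. The sum is 1+1+1+2+2+1+1 = 9, which reproduces the stated range. The sum is the same whichever sex has the point, so a range check will not find the reversal.

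Sex item as written minus sex item of the named score: men 1 − 0 = +1; women 0 − 1 = −1. The two sexes move 2 points relative to each other.

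For a group with female share f, the mean shifts by (1 − f) − f = 1 − 2f. The documents give no f. Assumed values:

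| f | Shift in mean score |
|---|---|
| 0.40 | +0.20 |
| 0.45 | +0.10 |
| 0.50 | 0 |

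Two treatment groups with 40% and 45% women would therefore show a spurious mean difference of 0.20 − 0.10 = 0.10 points. Groups balanced on sex would show none.

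Effect on the propensity score: score as written = correct score + 2 × male − 1. If sex is also a linear term, the two models span the same space and give the same fitted values. A logistic model on 20,000 simulated patients confirmed this: the largest difference in fitted propensity was about 2 × 10⁻¹⁶ with sex in the model and 0.07 with sex left out. The 0.07 belongs to that simulated example and is not a forecast for this study.

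**2. Hypertension.** Entries of Table 4 side by side:

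- Hypertension row: ICD-10 E10-E13, E15.
- Renal impairment row: includes E10.2, E11.2 and E13.2, and also I12.0, I13.1 and I13.2.
- Chronic kidney disease row: describes the expanded renal list as covering diabetes with kidney complications and hypertensive nephropathy, among others.

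On the protocol's own usage, E10, E11 and E13 are diabetes codes, and hypertensive disease sits in the I block. E12 and E15 appear nowhere else in the protocol, so the internal evidence covers three of the five. The run 10-13, 15 matches I10-I13, I15 with one letter changed.

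Two consequences follow. Hypertension reimbursed under an ICD-10 code is missed. A group C prescription reimbursed under E10-E13 counts as hypertension, and group C in Table 4 extends to lipid-modifying drugs (C10).

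The ICPC arm (K86, K87) still works. If a share s of antihypertensive reimbursements carries an ICD-10 code, a share 1 − s is recognised. The documents do not give s; assumed values of 25%, 50%, 75% and 90% give 75%, 50%, 25% and 10%. These are shares of reimbursements, not of patients: one qualifying dispensation in the year is enough for the score items.

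**3. Antiplatelets.** Prefix check, with study-drug codes from Table 2 (section 9.1) and the other two from Table 4:

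| Drug | ATC | Matches B01A | Matches B01AC |
|---|---|---|---|
| Warfarin | B01AA03 | yes | no |
| Apixaban | B01AF02 | yes | no |
| Rivaroxaban | B01AF01 | yes | no |
| Dabigatran | B01AE07 | yes | no |
| Heparin | B01AB | yes | no |
| Aspirin | B01AC06 | yes | yes |

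B01A matches 4 of 4 study drugs and B01AC matches 0 of 4. A non-aspirin flag also needs B01AC06 removed.

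What B01A picks up depends on the window, and neither section 9.6 nor 9.7 says whether the index date counts. If it does, every cohort 1a patient is positive and the covariate is constant. If only the 365 days before index count, the OAC-naïve criterion keeps the study drugs out, but heparin and aspirin remain. A longer look-back would also admit OAC use that ended more than 365 days before index.

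**4. Age band.** CHA2DS2-VASc gives one point from age 64, while modified HAS-BLED in the same table cuts at 65. Patients aged 64 gain a point in one score only.

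**The case against.** The strongest reply is that little of this reaches the primary comparison. Much of that stands. Gender is its own covariate, so the sex reversal can vanish from the propensity score. Antihypertensive drug classes (C02, C03, C07, C08, C09) and aspirin are separate rows. Modified HAS-BLED, itself a covariate, names B01AC in its own definition, so the B01A entry does not enter that score despite the note in its row. A reader might infer that hypertension and antiplatelet treatment are left unbalanced after matching. The documents do not support that: the flags are misclassified, with partial capture elsewhere.

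Other stronger readings also fail:

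- That every total CHA2DS2-VASc score is off by exactly 1. This holds for the sex item alone; the hypertension and age items can add to or offset it.
- That any diabetic on a group C drug becomes hypertensive. The diabetes code must be the reimbursement code on that group C prescription.
- That B01A necessarily captures the study drugs. This depends on the window.
- That prior myocardial infarction must be added to the vascular item. Table 4 is consistent in using peripheral artery disease alone.

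It can also be said that the direction of the sex point comes from the published score and not from the protocol. That is so, but the protocol uses the score's name without qualification, whereas it labels its HAS-BLED as modified. Finally, the aspirin row prints its code with a space after B01A, so the antiplatelet code may have lost its last letter. That is possible but unproven, and the entry would be wrong either way.

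**Conclusion.** The three entries are wrong as written and should be corrected before any programming.

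- **Sex item:** wrong by 1 point for every patient, 2 points between the sexes. It corrupts the reported CHA2DS2-VASc and its use as effect modifier. It leaves the propensity score unchanged if sex is a separate linear term. This rests on the standard definition of the named score.
- **Hypertension:** misclassified in both directions, with the error carried into both risk scores. The size cannot be derived from the documents, because the split between ICD-10 and ICPC reimbursement codes is not given.
- **Antiplatelets:** the stand-alone covariate contradicts its own label and the B01AC code in modified HAS-BLED. It is either constant or a mixture with heparin and aspirin, depending on the window. This is provable from the protocol alone.

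The case for correction is that the codes are wrong and a secondary objective reports the scores. It does not depend on any demonstrated bias in the primary incidence rate ratios.

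**What to change.** In Table 4:

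1. CHA2DS2-VASc sex item: female = 1, male = 0.
2. Hypertension: replace E10-E13, E15 by I10-I13, I15; keep K86 and K87.
3. Non-aspirin antiplatelets: replace B01A by B01AC excluding B01AC06, and state whether the index date lies inside the co-medication window.
4. CHA2DS2-VASc age band: start at 65, in line with the cut used in modified HAS-BLED.

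Then derive both scores and all three propensity models from the corrected list.

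The cost is an edit to a code list. Section 9.4 already has ATC codes, reimbursement codes and ICD-10 diagnoses being retrieved, so no new data are needed. Correcting later would mean re-deriving scores, refitting the propensity models and possibly rematching.
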